**7.2. Secondary Efficacy Analyses**

**7.2.1. Endpoint / Variables**

- Rate of change in log10CFU per ml direct respiratory sputum samples over the period baseline to Day 2 (EBA CFU0-2).
- Rate of change in log10CFU per ml direct respiratory sputum samples over the period Day 2 to Day 14 (EBA CFU2-14).
- Rate of change in time to sputum culture positivity (TTP) over the time period baseline to Day 14 (EBA TTP0-14)

- Rate of change in time to sputum culture positivity (TTP) over the time period baseline to Day 2 (EBA TTP0-2)
- Rate of change in time to sputum culture positivity (TTP) over the time period Day 2 to Day 14 (EBA TTP2-14)

### **7.2.2. Summary Measure**

Mean daily rate of change in log10CFU or TTP for each treatment group.

### **7.2.3. Population of Interest**

The secondary efficacy analyses will be based on the efficacy population, unless otherwise specified.

### **7.2.4. Strategy for Intercurrent (Post-Randomization) Events**

The treatment effect to be estimated will be the while on treatment effect of initial randomised treatment.

All applicable recorded data up to the time of study withdrawal will be included in the analysis, regardless of discontinuation of study medication.

### **7.2.5. Statistical Analyses / Methods**

Details of the planned displays are provided in [Appendix 10: List of Data Displays](#) and will be based on GSK data standards and statistical principles.

Unless otherwise specified, endpoints / variables defined in Section [7.2.1](#) will be summarised using descriptive statistics, graphically presented (where appropriate) and listed.

### 7.2.5.1. Statistical Methodology Specification

Endpoint

 
• Rate of change in log10CFU per ml direct respiratory sputum samples over the period baseline to Day 2.
 
• Rate of change in time to sputum culture positivity (TTP) over the time period baseline to Day 2 (EBA TTP0-2)
 

Model Specification

 
• Mixed models repeated measures analysis.
 
• Terms in the model: 
 
• Response: log10CFU or TTP as appropriate
 
• Categorical: treatment
 
• Continuous: time, BMI
 
• Interaction: treatment*time.
 
• Random: Subject
 
 
 
• Efficacy population
 
• Data from the standard of care arm will be pooled for the analysis.
 

Model Checking & Diagnostics

 
• Normality assumptions underlying the model used for analysis will be examined by obtaining a normal probability plot of the residuals and a plot of the residuals versus the fitted values (i.e. checking the normality assumptions and constant variance assumption of the model respectively) to gain confidence that the model assumptions are reasonable.
 
• If there are any departures from the distributional assumptions, alternative models will be explored using appropriate transformed data (e.g. log transformation (to base 10 for TTP), square root).
 

Model Results Presentation

 
• Summary of the mean, standard deviation, standard error and associated 95% confidence interval for each treatment arm.
 

Subgroup Analyses

 
• No subgroup analyses are planned for this endpoint.
 

Sensitivity and Supportive Analyses

 
• No sensitivity or supportive analyses are planned for this endpoint.
 

Endpoint

 
• Rate of change in <math>\log_{10}</math>CFU per ml direct respiratory sputum samples over the period Day 2 to Day 14.
 
• Rate of change in time to sputum culture positivity (TTP) over the time period baseline to Day 14 (EBA TTP0-14)
 
• Rate of change in time to sputum culture positivity (TTP) over the time period Day 2 to Day 14 (EBA TTP2-14)
 

Model Specification

 
• As described for the primary endpoint, see Section 7.1.5, except: 
 
○ For the models for Days 2-14, baseline <math>\log_{10}</math>CFU (or baseline TTP for TTP (2-14) should be included as a continuous covariate.
 
 
 
• For the TTP endpoints, the data may be log transformed using base 10 if the residuals do not follow a normal distribution.
 

Model Checking & Diagnostics

 
• As described for the primary endpoint, see Section 7.1.5.
 

Model Results Presentation

 
• As described for the primary endpoint, see Section 7.1.5.
 

Subgroup Analyses

 
• No subgroup analyses are planned for these endpoints.
 

Sensitivity and Supportive Analyses

 
• No sensitivity or supportive analyses are planned for these endpoints.
 

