**7.1.5.1. Statistical Methodology Specification**

Endpoint

 
• Rate of change in log10CFU per ml direct respiratory sputum samples over the period baseline to Day 14.
 

Model Specification

Model 1:
 
 
• Mixed model repeated measures analysis. Terms in the model:             
 
• Response: log10CFU
 
• Categorical: treatment
 
• Continuous: time, BMI
 
• Interaction: treatment*time
 
• Random: Subject
 
 
 
 
Model 2:
 
In addition, to characterize any bi-linear characteristics a bi- linear Bayesian regression model of the following form will also be fitted:
 $y_i = \begin{cases} \text{normal}(\alpha + \beta_1(t_i - cp), \sigma^2) & \text{if } t_i < cp \\ \text{normal}(\alpha + \beta_2(t_i - cp), \sigma^2) & \text{if } t_i \geq cp \end{cases}$ 
 
• Where cp=change (node) point as determined by the data (separate nodes for each treatment group), and t=time.
 
• The model will include terms for intercept, BMI, treatment, treatment*day before node, treatment*day after node, subject.
 
• This model would utilize uninformative uniform priors for cp and <math>\sigma^2</math> (discrete uniform(2,13) and uniform(0,5) respectively) and uninformative normal priors for the intercept, treatment, baseline log10CFU and BMI (normal(0,var=1000000)). Subject will be a random effect with an uninformative prior (normal(0,var), where var=uniform(0,5)).
 
• The efficacy population will be used for both models.
 
• Data from the standard of care arm will be pooled for the analysis.
 
• Where CFU plate counts are Too Numerous To Count (TNTC) a value of 2500 should be imputed for both models.
 

Model Checking & Diagnostics

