**12.6.3. Efficacy**

Efficacy
CFU

 
• Baseline CFU will be calculated as: Mean (log10(CFU Day -1), log10(CFU Day -2))
 
• Log(CFU) will be calculated as: Log(CFU/ml) = log10(mean(Total count 1:Total Count 2)*2*5*10^Dilution)
 

Efficacy

where:
 
 
• Total count 1 and total count 2 are the bacterial counts from plates 1 and 2 respectively. Where plate counts are reported as Too Numerous To Count (TNTC), a value of 2500 will be imputed. If a count is only available for 1 plate, then that count will be used instead of the mean.
 
• Dilution is the dilution factor for that plate.
 
• In the calculation, the *2 represents the 1:1 dilution of the original specimen and the *5 represents the 0.2 ml (200 µl) inoculation of the specimen.
 
• For bacteria counts with a comment of "Half of plate X was contaminated so only half the plate was counted", the count for that plate will be doubled for the analysis.
 

TTP

 
• The mean of the time to positivity for both plates (plate 1 and plate 2) at each timepoint will be calculated and used in any derivation of summary statistics and analyses. If a result is only available for 1 plate, then that value will be used instead of the mean. Where listed, all data will be presented.
 

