**CONFIDENTIAL**

201214

2.8.	Efficacy	Non-standard EFF_T1	Summary Table of Change from Baseline in TTP Counts Over Time	Include baseline row similar to LB1 template.	SAC
2.9.	Efficacy	Non-standard EFF_T2	Rate of Change in TTP –Mixed Model Analysis	Supportive SAS output to be produced and archived	SAC
2.10.	Efficacy	Non-standard EFF_T3	Node and Slope Parameter Estimates for TTP by Treatment –Bi-linear Bayesian Model Analysis	For endpoint TTP(0-14) only. Supportive SAS output to be produced and archived	

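### Table 2.10 fits the bi-linear Bayesian model to TTP with variance priors scaled for log10CFU; in hours they cap both SDs at 2.24 h and can make the slope intervals far too narrow

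*SAP*

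**What the plan says.** SAP 7.1.5.1 writes Model 2 for log10CFU over Days 0-14. The node and the residual variance σ² receive priors that the SAP calls uninformative: "discrete uniform(2,13) and uniform(0,5) respectively". The subject effect is handled the same way: "Subject will be a random effect with an uninformative prior (normal(0,var), where var=uniform(0,5" (closing brackets omitted). Both uniform(0,5) priors are on variances, and the prior list names baseline log10CFU as a covariate.

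For TTP0-14, SAP 7.2.5.1 gives the model specification as "As described for the primary endpoint, see Section 7.1.5, except", followed by one exception: a baseline covariate in the Day 2-14 models. A second bullet allows a transformation: "For the TTP endpoints, the data may be log transformed using base 10 if the residuals do not follow a normal distribution". No priors specific to TTP appear anywhere.

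SAP 12.10.5 lists Table 2.10 as "Node and Slope Parameter Estimates for TTP by Treatment", from the bi-linear Bayesian model, with the programming note "For endpoint TTP(0-14) only".

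On scale, SAP 12.6.3 log10-transforms CFU but takes TTP as a plain average: "The mean of the time to positivity for both plates (plate 1 and plate 2) at each timepoint will be calculated and used". The listing shell EFF_L1 shows TTP in hours, and protocol 3.1 describes the TTP measure in hours per day.

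**The concern.** A uniform(0,5) prior on a variance is loose or tight depending on the unit of the response. For log10CFU it is loose. For TTP in hours it says that neither the within-participant scatter nor the spread between participants can exceed 2.24 h, which is a strong statement to make under the label uninformative.

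If the data are more variable than that, the residual variance posterior piles up at 5, and the slope intervals are computed as if the residual SD were 2.24 h. Model 2 as written has one σ² for all arms, so every arm's interval shrinks together, and dose groups in Table 2.10 can look more clearly separated than the data support.

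Nothing in the plan reliably catches this. The log10 option is triggered by the shape of the residuals, not by their size, so normal residuals with a large SD stay in hours. The written Model 2 criteria in SAP 7.1.5.1 are well-mixed chains and agreement between independent runs within twice the Monte Carlo standard error. A chain pressed against a bound can mix well, and a second run under the same prior reproduces the same answer.

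**Working it through.** **The cap.** The upper limit of both variance priors is 5, so the largest SD allowed is √5 = 2.236 in the unit of the response.

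**The priors do suit CFU.** Protocol 10.1.2 gives SDs of the daily change in log10CFU of 0.049 to 0.067, where the daily change is the Day 14 change divided by 14. Multiplying back, 0.049 × 14 = 0.69 and 0.067 × 14 = 0.94; the variances are 0.47 and 0.88, well below 5. No equivalent figure exists for TTP, and the documents state no TTP SD, so there is no figure of the plan's own to reproduce. Every TTP SD below is an assumption.

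**First-order effect.** When the cap binds, interval width is too small by the factor r = max(1, s/√5), where s is the true residual SD. Coverage of a nominal 95% interval is then 2Φ(1.96/r) − 1.

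**Simulation with the node unknown.** One arm of 9 participants (the reduced size in protocol 10.1.2) or 15; baseline as Day 0 and the planned sampling Days 1, 2, 3, 4, 6, 8, 10, 12 and 14. Assumed truth: node at Day 4, slopes 8 then 4 h/day, between-participant SD 2, 10 or 30 h. The model had a random subject intercept, no BMI term, the SAP's discrete uniform(2,13) node prior and flat priors on intercept and slopes. The posterior was computed on an exact grid, with 95% HPD intervals and 900 data sets per setting. Ranges cover both slopes and the settings run.

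| Assumed residual SD (h) | r | First-order coverage | Simulated, capped, n = 9 | Simulated, capped, n = 15 |
|---|---|---|---|---|
| 2 | 1.00 | 95% | 95-97% | 94-98% |
| 3 | 1.34 | 86% | 82-85% | 83-86% |
| 6 | 2.68 | 53% | 46-52% | 45-49% |
| 12 | 5.37 | 29% | 22-27% | 21-28% |
| 24 | 10.73 | 14% | not run | not run |

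With a wide variance prior, coverage at n = 9 was 92-99%. At SD 6 h and n = 9, the median after-node interval was 0.33-0.34 h/day wide with the cap and 1.12-1.15 h/day without it, a factor of 3.4. With the cap, the posterior mean of σ² averaged 4.85-4.99 in every setting with SD 3 h or more.

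**Second, separate simulation.** 9 participants, node at Day 5, same slopes, 80 data sets per setting. Coverage (before node / after node):

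| Residual SD / between-participant SD (h) | SAP prior | Non-binding prior |
|---|---|---|
| 1.5 / 1.5 | 98% / 96% | 98% / 96% |
| 2 / 10 | 96% / 98% | 94% / 95% |
| 5 / 5 | 56% / 58% | 95% / 95% |
| 10 / 20 | 28% / 30% | 95% / 99% |
| 20 / 40 | 13% / 13% | 94% / 96% |

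The 2 / 10 row separates the two caps. There the subject cap binds and the residual cap does not, and the slope intervals are not narrowed (before-node width 0.74 h/day against 0.72). The harm to the slopes comes from the residual cap.

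**On log10(TTP).** By the delta method the variance is (s/(TTP × ln 10))². With an assumed TTP of 100 to 250 h, s = 3 h at 250 h gives (3/575.6)² = 0.00003, and s = 24 h at 100 h gives (24/230.3)² = 0.011. A bound of 5 would not bind.

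**The case against.** **Whether Model 2 is planned for TTP at all.** SAP 7.2.5.1 ends by stating that no sensitivity or supportive analyses are planned for these endpoints, while SAP 2.1 calls Model 2 supportive. That statement sits under the separate sensitivity heading, however. Model 2 belongs to the model specification that 7.2.5.1 imports, and Table 2.10 names it explicitly. The wording could be tidier, but the plan to fit it is clear enough.

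**Whether the scale is hours.** No output shell fixes the Model 2 unit for TTP: EFF_T3 shows only CFU rows. Protocol 9.1 describes EBA TTP0-14 as a percentage rate of change, which suits a log scale. This is fair, and it supports the first remedy below. But as the SAP is written, untransformed hours are the default and log10 is optional.

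**Whether diagnostics would force a transformation or reveal the problem.** The rule stated for the Day 0-2 endpoints, "If there are any departures from the distributional assumptions, alternative models will be explored using appropriate transformed data", has a counterpart under Model 1 in SAP 7.1.5.1 that reaches TTP0-14 by reference and covers non-constant variance as well as non-normality. That narrows the gap, but residuals that are normal and homoscedastic with a large SD still pass. Trace plots of all parameters must be inspected, and a σ² chain sitting just under 5 would be noticeable to an attentive reader. Table 2.9 also offers an uncapped comparison. Neither amounts to a required check.

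**Importance.** The true SD is unknown, the coverage figures are illustrations, the study makes no formal hypothesis tests, and no decision rule uses Table 2.10. All of this stands, and it limits the reach of the point without removing it.

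**Conclusion.** The concern holds. Followed as written on the default scale, the SAP caps the residual and between-participant SDs of TTP at 2.24 h. Whenever the residual SD exceeds that, the slope intervals in Table 2.10 are too narrow by roughly SD/2.24. At or below 2.24 h there is no effect.

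The conclusion rests on two conditions: TTP is analysed in hours, and its residual SD is above 2.24 h. The first is the SAP's default; the second cannot be settled from the documents.

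The reach is one supportive table for one secondary endpoint. The mixed-model TTP results in Table 2.9 carry no such cap, the CFU analyses are on the scale the priors were written for, and the dose-escalation model outputs use CFU(0-14) only. The change is worth making before the final analysis, but it does not threaten the primary result.

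**What to change.** For Table 2.10, adopt one of two options in SAP 7.2.5.1:

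- Pre-specify log10(TTP) as the Model 2 response and keep uniform(0,5). This agrees with the percentage scale in protocol 9.1; report each slope as 100 × (10^slope − 1) % per day.
- Keep hours and state residual and subject variance priors wide enough for that scale.

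Under either option, add a line to the Model 2 diagnostics requiring confirmation that no variance posterior sits at its prior bound. State one TTP scale for both protocol 9.1 and the SAP displays.

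The cost is a few lines of SAP wording and, under the first option, a back-transformation in Table 2.10. Data collection, Model 1, Table 2.9 and the dose-escalation outputs do not change.

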### **7.3. Exploratory Efficacy Analyses**

#### **7.3.1. Endpoint / Variables**

CCI

These exploratory endpoints will be analysed and reported separately.

## **8. SAFETY ANALYSES**

The safety analyses will be based on the Safety population, unless otherwise specified.

### **8.1. Adverse Events Analyses**

Adverse events analyses including the analysis of adverse events (AEs), Serious (SAEs) and other significant AEs will be based on GSK Core Data Standards.

### **8.2. Clinical Laboratory Analyses**

Laboratory evaluations including the analyses of Chemistry laboratory tests, Haematology laboratory tests, Urinalysis, and liver function tests will be based on GSK Core Data Standards.

### **8.3. Other Safety Analyses**

The analyses of non-laboratory safety test results including ECGs and vital signs will be based on GSK Core Data Standards, unless otherwise specified.

Listings of the troponin data and mycobacterial data will be produced.

## 9. PHARMACOKINETIC ANALYSES

### 9.1. Secondary Pharmacokinetic Analyses

#### 9.1.1. Endpoint / Variables

Derived PK parameters: AUC(0-t) or AUC(0-24), Cmax, tmax and Cτ.

#### 9.1.2. Summary Measure

- Dose proportionality of AUC(0-t) or AUC(0-24)
- Dose proportionality of Cmax
- Achievement of Steady State (Cτ)
- Summary statistics for tmax

#### 9.1.3. Population of Interest

The PK analyses will be based on the PK population, unless otherwise specified.

#### 9.1.4. Strategy for Intercurrent (Post-Randomization) Events

- The treatment effect to be estimated will be the while on treatment effect of actual received treatment.
- All applicable recorded data up to the time of the intercurrent event will be included in the analysis.

#### 9.1.5. Statistical Analyses / Methods

Unless otherwise specified, endpoints / variables defined in Section 9.1.1 will be summarised using descriptive statistics, graphically presented (where appropriate) and listed.

For each of the parameters Cmax, tmax, AUC(0-t), AUC(0-24), Cτ the following summary statistics will be calculated and tabulated by dose group:

- Untransformed data: N, n, arithmetic mean, 95% confidence interval (CI) for the arithmetic mean, SD, median, minimum, maximum

The following additional summary statistics will be calculated and tabulated by dose group, for the parameters Cmax, AUC(0-t), AUC(0-24) and Cτ.

- Log-transformed data: Geometric mean, 95% CI for the geometric mean, SD, between participant coefficient of variation (%CVb)

%CVb will be calculated as:  $CV_b (\%) = \sqrt{(\exp(SD^2) - 1)} * 100$

Where SD = SD of loge transformed data

### 9.1.5.1. Statistical Methodology Specification

The following pharmacokinetic statistical analyses will only be performed if sufficient data are available (i.e. if participants have well-defined plasma profiles).

Endpoint

 
• Dose proportionality of AUC(0-t) or AUC(0-24)
 
• Dose proportionality of Cmax
 

Model Specification

 
• This will be analysed using a power model:  <math>y = \alpha * \text{dose}^\beta</math>            where <math>y</math> = PK parameter being analysed (i.e. AUC or Cmax) and <math>\alpha</math> = participant.
 
• Loge transformed data will be analysed by fitting the following terms in the mixed effect model:            Fixed, continuous effect: loge(dose)            Random effect: Participant
 
• The Kenward Roger method for approximating the denominator degrees of freedom and correcting for bias in the estimated variance-covariance of the fixed effects will be used.
 
• An unstructured (UN) covariance structure for the G matrix will be used.
 
• For AUC, AUC(0-24) will be analysed where calculable; where doses do not have quantifiable concentrations at 24 hours, AUC(0-t) will be analysed.
 
• PK population
 
• Data from at least three doses must be available to perform the dose proportionality analysis.
 
• A slope <math>\approx 1</math> implies dose proportionality
 

Model Checking & Diagnostics

 
• If the model does not converge, the random participant effect will be removed from the model.
 

Model Results Presentation

 
• Estimates of the mean slopes of loge(dose) will be reported along with corresponding 90% confidence intervals.
 
• A figure of log(dose) vs log(AUC) will be presented in the form of a scatterplot of all individual participant values, along with a regression line and associated 95% confidence interval. A similar plot will be produced for log(dose) vs log(Cmax).
 

Endpoint

 
• Achievement of Steady State (Cτ)
 

Model Specification

 
• This will be analysed using a mixed model:
 

Fixed effects:  $\log_e(\text{dose})$ , day,  $\log_e(\text{dose}) \cdot \text{day}$

Random effect: participant

Day will be treated as a continuous variable, dose as a categorical variable.

- The dose-by-day interaction will be tested for its significance at the 5% level, if the interaction is not significant then a single point estimate for all dose levels pooled will be calculated in addition to the individual dose levels.
- The Kenward Roger method for approximating the denominator degrees of freedom and correcting for bias in the estimated variance-covariance of the fixed effects will be used.
- An unstructured (UN) covariance structure for the G matrix will be used.
  - In the event that this model fails to converge, alternative covariance structures may be considered such as variance components (VC) or compound symmetry (CS).
  - Akaike's Information Criteria (AIC) will be used to assist with the selection of covariance structure.

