#### Weight

10. Body weight (in light clothing and with no shoes) between 40 and 90 kg, inclusive, at screening.

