	
Calculations will be based on the actual sampling times recorded during the study.
 
From the plasma concentration-time data, the following pharmacokinetic parameters will be determined, as data permit:
 
 
• maximum observed blood concentration (Cmax)
 
• time to Cmax (tmax)
 
• area under the plasma concentration-time curve [AUC0-t and AUC0-24]
 
• trough concentration (Cτ).
 
 
AUC0-t or AUC0-24 and Cmax may be used for assessment of dose proportionality. Trough concentration (Cτ) samples collected on the specified days will be used to assess attainment of steady state.
 
Pharmacokinetic data will be presented in graphical and/or tabular form and will be summarized descriptively.
 
Statistical analyses of the pharmacokinetic parameter data will be the responsibility of Statistics, Programming and Data Strategy (SPDS), GlaxoSmithKline. Distributional assumptions underlying the statistical analyses will be assessed by visual inspection of residual plots. Normality will be examined by normal probability plots, while homogeneity of variance will be assessed by plotting the residuals against the predicted values for the model. Alternative analyses of the data will be performed if any of the model assumptions appear to be violated. Full details on the statistical aspects will be detailed in the Reporting and Analysis Plan (RAP).
 
Dose Proportionality
 
Dose proportionality will be assessed via analyses of AUC0-t or AUC0-24 and Cmax. A statistical analysis will be performed using the power model. The analysis will be performed on loge-transformed data. For each of these parameters a mixed effects model will be fitted with loge (dose) as a fixed effect and individual subject fitted as random effects. Estimates of the mean slopes of loge (dose) will be reported along with corresponding 90% confidence intervals (slope≈1 implies dose proportionality).
 
Achievement of Steady State
 
Trough concentration levels, Cτ, collected pre-morning dose will be plotted by collection day and dose. To evaluate whether steady state was achieved, statistical analysis of Cτ will be performed after a log-transformation of the dose data. A mixed effect model will be fitted with dose, day and dose-by-day interaction as fixed effects (with dose as a factor and day as a continuous covariate) and subject as a random effect. The coefficients of the

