### 2.3. Study Design

Overview of Study Design and Key Features	
<pre> graph LR     A[SCREENING from -9 days prior to first dose] --> B[14-Day treatment period - GSK3036656]     A --> C[14-Day treatment period - Rifafour]     B --> D[Day 15 start/continue Rifafour*]     C --> D     D --> E[Follow-up at Day 28]             </pre> 
*This is not part of the study but is the post-study definitive treatment of TB.
	
Design Features	
 
• A single-centre, open-label trial in up to five sequential cohorts.
 
• Each cohort will involve participants being randomised to one of two possible treatments: either GSK3036656 or Standard-of-Care (SoC) regimen (e.g. Rifafour®e-275) for rifampicin-susceptible (drug sensitive) tuberculosis (DS-TB).
 
• Screening will be performed on days -9 to -1, followed by 14 days of once daily dosing and a follow-up visit 28 days after the first dose.
 
• All laboratory staff involved in analysing and reporting the primary and secondary change in CFU counts and TTP endpoint results will be blinded to treatment allocation.
 

Dosing	
 
• Once daily repeat dosing for 14 days.
 
• The starting dose for the GSK3036656 arm is a 15mg loading dose on Day 1 and 5mg maintenance dose on Days 2-14, given orally. The study will employ dose escalation, where the GSK3036656 dose for each cohort will be decided based on reviews of preliminary safety, tolerability and pharmacokinetic data; in addition, efficacy data will be considered if available.
 

Time & Events	
 
• See Appendix 2: Schedule of Activities
 

Treatment Assignment	
 
• 12-20 participants in each cohort (excluding possible replacements), randomised 3:1 to GSK3036656 or Standard of Care respectively.
 
• GSK RandAll NG will be used to generate the randomisation schedule.
 

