#### Dose Escalation

#### Pharmacokinetic (PK) Analysis

Dose escalation will primarily be based on population PK modelling.

The population PK model will be a fit for purpose model. Candidate model selection will be primarily based on a significant reduction in the objective function value ( $\geq 3.32$ ,  $\chi^2 < 0.05$ ) and improvement in the fits of diagnostic scatter plots. Inter-individual variability will be modelled using an exponential error model and residual error will be described by a proportional, proportional plus additive, or additive error model, depending on the data. Model performance will be evaluated using a visual predictive check. Simulations for dose recommendations will be conducted to determine the probability of an individual participant exceeding the defined exposure margins for  $AUC_{0-24}$  (4.9  $\mu\text{g}\cdot\text{h}/\text{mL}$ ) and  $C_{\text{max}}$  (0.443  $\mu\text{g}/\text{mL}$ ).

Alternatively, if a population PK model is not feasible, dose escalation will be based on a dose-exposure model of the form:

$$\log(\text{AUC}) = a + b \cdot \log(\text{DOSE}) + c \cdot \log(\text{BWT}/70)$$

$$\log(\text{C}_{\text{MAX}}) = d + e \cdot \log(\text{DOSE}) + f \cdot \log(\text{BWT}/70)$$

where a and d are AUC and  $C_{\text{max}}$  values, respectively; c = -0.75 and f = -1.00 are set values for allometric scaling; and b and e are scaling factors for dose proportionality.

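### The dose-proportionality slopes for AUC and Cmax leave out body weight, so their 90% intervals are wider than needed and would be biased by any weight trend across dose cohorts

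*SAP*

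**What the plan says.** For dose proportionality, SAP 9.1.5.1 fits a power model on the log scale. The fixed part is "Fixed, continuous effect: log e (dose") and nothing else; participant is a random effect. Protocol 10.3.1 agrees: "a mixed effects model will be fitted with log e (dose) as a fixed effect and individual subject fitted as random effects". The slope is reported with a 90% confidence interval (Table 4.4) and read as proportional if it is about 1. No margin is set. At least three doses are required.

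Elsewhere the plan relates the same exposures to dose and weight together. SAP 3.1 and Protocol Section 11 give equations for log AUC and log Cmax in log dose and log(BWT/70), in which "c = -0.75 and f = -1.00 are set values for allometric scaling; and b and e are scaling factors for dose proportionality". They are a fallback: "Alternatively, if a population PK model is not feasible, dose escalation will be based on a dose-exposure model of the form".

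On design, SAP 2.3 describes "A single-centre, open-label trial in up to five sequential cohorts" and states that "Each cohort will involve participants being randomised to one of two possible treatments", namely GSK3036656 or standard of care. Eligible weight is wide: "Body weight (in light clothing and with no shoes) between 40 and 90 kg, inclusive, at screening". Weight is recorded with vital signs from screening (Schedule of Activities, footnote E), and screening weight is used to derive BMI (SAP 12.6.2). BMI is a covariate for CFU and TTP (SAP 5.3). No body-size term is planned for the PK parameters.

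**The concern.** Randomisation is to drug or standard of care within a cohort, never between doses, so nothing in the design balances weight across dose levels. The plan's own equations take weight to affect both AUC and Cmax. A model with dose alone leaves that variation in the residual, which widens the interval. If average weight also rises or falls with dose, part of the weight effect is read as a departure from proportionality. At stake is the precision, and possibly the accuracy, of the two slopes in Table 4.4.

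**Working it through.** The documents state no precision or power for this slope, so there is no figure to reproduce.

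**Inputs from the documents.** Maintenance doses 5, 15 and 30 mg (SAP 5.1). Up to 15 on drug per cohort, reduced to 9 for ongoing and later cohorts (Protocol 5.1 and 10.1.2). Weight range 40-90 kg. Weight exponents -0.75 (AUC) and -1.00 (Cmax).

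**Assumed, not in the documents.** Group sizes 15/15/9; SD of log weight 0.15-0.20; residual SD of log exposure, after weight, 0.20-0.30.

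**Estimator.** Each participant gives one Day 14 AUC and one Cmax, so the random participant effect cannot be separated from the residual and does not remove weight. Least squares on the log scale is equivalent.
- Mean log dose = (15 × 1.609 + 15 × 2.708 + 9 × 3.401)/39 = 2.445. The sum of squared deviations of log dose is Sxx = 19.74.
- Half-width of the 90% interval = t(37) × s/√Sxx, where s is the SD of log exposure at a given dose. At a total CV of 30%, s = √ln(1 + 0.3²) = 0.294, which gives 1.687 × 0.294/√19.74 = 0.112.

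**Scale of the weight effect.** Under the set exponents, 90 kg against 40 kg changes AUC by (90/40)^0.75 = 1.84-fold and Cmax by 90/40 = 2.25-fold. These are the extremes of eligibility, not the likely spread.

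**Width, no weight trend.** Before the cost of estimating the coefficient, the dose-only interval is wider by √(1 + c²·SDw²/SDr²), where c is the weight exponent, SDw the SD of log weight and SDr the residual SD. For Cmax at 0.15 and 0.30 this is √(1 + 0.0225/0.09) = 1.12. Estimating the coefficient, and truncating weights to 40-90 kg, brings it to about 1.09. Simulated mean half-widths:

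| Parameter | SD log weight | Residual SD | Dose only | With weight | Wider by |
|---|---|---|---|---|---|
| AUC | 0.15 | 0.20 | 0.085 | 0.076 | 12% |
| AUC | 0.20 | 0.30 | 0.122 | 0.114 | 7% |
| Cmax | 0.20 | 0.20 | 0.099 | 0.076 | 30% |
| Cmax | 0.15 | 0.30 | 0.125 | 0.115 | 9% |

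Over all four SD combinations the range is about 5-18% for AUC and 9-30% for Cmax. The dose-only slope averages 1.00 and its interval covers about 90%.

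**Where the gain disappears.** With 7 per cohort (the minimum PK data for escalation), total CV 40% and SD of log weight 0.10, fitting weight makes the AUC interval about 1% wider.

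**Bias, if weight trends with dose.** The shift in the slope is c times the regression slope of log weight on log dose. With the 5 mg cohort 10% lighter, that regression slope is 15 × (1.609 - 2.445) × ln(0.9)/19.74 = 0.067.
- AUC: 1 - 0.75 × 0.067 = 0.95. Cmax: 1 - 1.00 × 0.067 = 0.93.
- Truncation at 40 kg pulls the lighter cohort's mean back up. The simulated slopes are then about 0.96 and 0.94-0.95, with coverage of the 90% interval about 72-85%. With weight fitted they are 1.00 and about 90%.
- A trend the other way shifts the slope upwards.

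**The case against.** A dose-only power model is a legitimate descriptive summary, and the protocol specifies it. Most of the case for leaving it stands.

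- **A reader might infer that the reported slope is biased because dose is not randomised.** The documents do not support that. Bias needs weight to trend with dose. The weight criterion is the same for every cohort, there is one centre, and nothing reported shows such a trend. The 10%-lighter cohort is an illustration.
- **A reader might infer that the SAP contradicts itself by defining one slope in two ways.** That also goes too far. The weight equations serve dose escalation, and only if population PK modelling is not feasible. They may never be fitted. The population PK analysis has its own plan, which may handle weight.
- **The exponents are set values, not estimates for this drug.** Clearance is mainly renal (Protocol 3.3.1 and 5.6), so weight is not the only candidate covariate. This tells against making a slope with fixed exponents the main result.
- **The absolute gain is small.** For AUC it is 0.008-0.009 of half-width in the rows above. With no margin, slopes of 0.94-0.96 would still be read as about 1.
- **The two harms partly offset each other.** When weight is correlated with dose, adjusting for it costs precision. In the AUC case with SDs of 0.15 and 0.30, without truncation, the width penalty falls from about 5% to 0.5%.

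None of this is a reason to ignore a baseline value already collected on everyone. It limits the size of the point and the form of the remedy.

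**Conclusion.** The point holds as a minor one. Both documents leave weight out of a regression across cohorts that were not randomised to dose. If weights differ only by chance, the slope and its coverage are sound and the loss is precision: about 5-18% of interval width for AUC and 9-30% for Cmax under the assumed SDs, and little or nothing with few participants, high CV or little weight spread. If weight trends with dose, the slope is also biased, by about 0.04 (AUC) and 0.05-0.06 (Cmax) for a 10% lighter lowest-dose cohort. All of these sizes assume the plan's set exponents and SDs that the documents do not give. The analysis is secondary and descriptive, so no study decision depends on it.

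**What to change.** In SAP 9.1.5.1 and Table 4.4:
- Add a second power model with log_e(screening weight/70) as a continuous fixed covariate and an estimated coefficient. Report its slope and 90% interval next to the protocol's dose-only slope.
- Use the set exponents -0.75 and -1.00 only in a sensitivity fit.
- Summarise screening weight by dose group, so that a trend with dose can be seen.
- Record the addition in SAP 2.1 as a departure from Protocol 10.3.1.

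The cost is one degree of freedom, one extra fit per parameter (plus the sensitivity fit) and a few lines of SAP text. No new data are needed.
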